### 14.3.3 Targeting & Lead Placement

Targeting is accomplished by combining high resolution 3T MRI images with thin cut CT scan images and the use of computerized targeting software. Images are uploaded into the targeting software. The computer then fuses both MRI and CT scans together. The operator of the computer is then able to identify certain

landmarks including the anterior commissure (AC) and posterior commissure (PC). The intercommissural length is then calculated. The actual target is then identified by using offsets from these structures. In the case of the periaqueductal grey, the X coordinate is 10mm posterior to the mid-commissural point, the Y coordinate is 2-3mm lateral to the wall of the IIIrd ventricle, and the Z coordinate is in the plane of the intercommissural line. T2 weighted images can then be used to further refine the target based on direct visualization of the periaqueductal grey.

Once the final target is identified, the computer yields an X,Y,Z coordinate for the stereotactic field. This is set on the CRW arc and used to deliver the lead.

#### 14.3.4 Macrostimulation and Sensing

Once the lead is at target, test stimulation will begin with an external neurostimulator (model # 37022). Macrostimulation will be performed by a Neurologist who specializes in neurophysiologic monitoring for deep brain stimulation. He has been involved in well over 700 similar procedures. The macrostimulation procedure involves an algorithm that tests all combinations of contacts in a bipolar fashion. Both pulse-width and frequency will be set at fixed values and amplitude will be gradually increased in steps while recording clinical effects. The goal will be to determine optimal settings for therapeutic effects as well as suboptimal settings that induce side effects. It should be noted that all effects from stimulation are fully reversible by cessation of stimulation or revision of programming parameters. Upon successful intraoperative macrostimulation, the implantable neurostimulator (model 37601) will be connected.

Therapeutic effect can be elicited by the patient reporting a warm feeling in various areas of the body. No such feeling, however, does not preclude optimal targeting. Chronic stimulation may be needed to induce a beneficial effect.

Likewise, changes in vital signs will also be assessed as these changes are indicative of autonomic effects. Examples would be change in heart rate, systolic blood pressure, etc.

Neurologic changes would also be assessed as the periaqueductal grey is close to the superior colliculus and thus various eye findings might be induced.

If the subject reports effects of DBS on sleep, the stimulation will be cycled in appropriate 12-hour on and off periods in a 4 week trial period and maintained if superior. Also, if the subject does not tolerate continuous stimulation for many hours, cycling at faster on and off periods will be tested.

In subjects with an implanted PC+S device, the visits at weeks 12, 16, 20, 24, 32, 40, 48 and 52 will include recording of local field potentials. Recording will be done from all contacts during DBS at optimal setting for pain relief, over a period of one minute.

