### 11.4 Secondary Objectives:

To assess the clinical effects of DBS on autonomic functioning when PAG/PVG stimulation is applied over many weeks (44 weeks); to determine with Aactiva PC+S whether local field potentials in the PAG/PVG can be used to predict the efficacy of DBS in this region.

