**17.2 Efficacy Analyses:**

To test the core hypothesis and secondary outcome measures, the analysis (descriptive) for efficacy trends will be conducted on the baseline through 52 weeks of data collection for all twelve (12) participants enrolled.

The one-minute recordings of local fields potentials from the bilateral or unilateral contacts PAG/PVG by the PC+S device will be analyzed in the time domain (autocorrelations and inter-lead cross-correlations) and the frequency domain (power in alpha, beta, gamma and delta EEG bands). Peaks in spectra or in auto- or cross-correlations will be examined for correlations with pain level (analgesia obtained) for each contact or pair of contacts. The potential ability shown by these results for usefulness in electrode targeting of future subjects (with pain from SCI or other causes) will be evaluated. That is, their

predictions of efficacy will be evaluated. These preliminary findings will be considered in the planning of studies with larger subject populations with pain of adequate statistical power.

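### Local field potentials are specified only during pain-optimised stimulation from week 12, so the planned analysis cannot test whether a signal present before activation predicts DBS efficacy

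*Combined protocol and SAP*

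**What the plan says.** The synopsis and section 11.4 set a secondary objective, for participants with the sensing (PC+S) device, of determining "whether local field potentials in the PAG/PVG can be used to predict the efficacy of DBS in this region".

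Section 14.3.4 says when and how the signal is taken: "the visits at weeks 12, 16, 20, 24, 32, 40, 48 and 52 will include recording of local field potentials", and "Recording will be done from all contacts during DBS at optimal setting for pain relief, over a period of one minute". Section 12.6.1 applies the first-year recording protocol to the extension, so no further recording condition is introduced there.

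Section 17.2 describes the analysis. Peaks in the spectra and correlation functions "will be examined for correlations with pain level (analgesia obtained) for each contact or pair of contacts". It then says of future use: "The potential ability shown by these results for usefulness in electrode targeting of future subjects" will be evaluated, glossed as meaning that their "predictions of efficacy will be evaluated". It also states the status of the results: "These preliminary findings will be considered in the planning of studies with larger subject populations".

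Section 12.3 explains how the setting is reached. It starts from a percentage of the threshold for unwanted effects and is re-adjusted monthly on the 0-10 pain score (NRS). At the first programming session, 12 to 48 hours after the generator is internalised, the NRS is taken with stimulation off and then contact by contact.

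Table 2 has one row that combines adjustment and/or sensing with a possible five-minute inactivation. Section 12.5 uses inactivation to look at placebo effects and at the safety and stability of the implant; LFPs are not mentioned.

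**The concern.** A predictor of efficacy is most useful if it can be measured before the treatment has acted. Here every specified LFP is taken after weeks of stimulation and at a setting tuned on the same kind of score that measures success. An association between such a signal and pain could arise because the signal forecasts benefit, because stimulation changed it, or because it follows current pain. The planned correlation cannot separate these.

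At stake is the reading of one secondary objective. If on-treatment correlations are reported as prediction, the larger studies that 17.2 has in mind could be planned around a marker that has not been shown to exist before stimulation. The missing recording also cannot be recovered: each participant has only one pre-activation period with the implanted system.

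**Working it through.** The plan gives no sample size, power or effect size for this objective, so there is no stated figure to reproduce. The check is a count and a comparison of sections.

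**Inputs**
- Recording weeks (14.3.4): 12, 16, 20, 24, 32, 40, 48, 52, which is 8 visits of one minute each.
- Start of long-term stimulation (Table 1, follow-up procedures): week 8.
- Table 2, adjustment and/or sensing row: stated total 9.

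**Timing.** Weeks since activation = recording week − 8:

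| Recording week | 12 | 16 | 20 | 24 | 32 | 40 | 48 | 52 |
|---|---|---|---|---|---|---|---|---|
| Weeks since activation | 4 | 8 | 12 | 16 | 24 | 32 | 40 | 44 |

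None is zero or negative, so 0 of 8 recordings precede activation. Table 2 marks long-term stimulation from week 9; using that instead, the first interval is 12 − 9 = 3 weeks and the count is still 0 of 8.

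**Condition.** Recordings specified with stimulation off: 0. Recordings specified at any setting other than the one chosen for pain relief: 0.

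**Table 2 against 14.3.4.** The marks in the row are week 8 (1), weeks 12 and 16 (2), weeks 20 and 32 (2), weeks 24, 40 and 48 (3) and week 52 (1): 1 + 2 + 2 + 3 + 1 = 9, as stated. The one occasion beyond the eight in 14.3.4 is week 8, which adjustment without sensing would explain. The two places are compatible, but neither says whether week 8 includes sensing.

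**Analysis.** 17.2 pairs the LFP with pain level and does not say whether the pain score is concurrent or later. Note 1 to Table 2 puts pain assessments before adjustments at a visit. If the optimal setting means the setting after adjustment, the score and the LFP from one visit could belong to different settings. The documents do not settle this.

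**Recording time per PC+S participant.** Now 8 × 1 = 8 minutes. With one week-8 recording, 8 + 1 = 9. With an off-state recording at all eight later visits as well, 8 + 1 + 8 = 17.

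**The case against.** The strongest reply is that prediction need not mean pre-activation. The objective sets no time for the signal, and seven recording visits follow week 12, so a week-12 LFP could be related to later relief. This stands in part. A reader might infer that the recordings have no predictive value at all, and the documents do not support that. But the forecast would apply to people already under treatment, and no such lagged analysis is written.

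Second, 17.2 works by contact and speaks of targeting, so its idea of prediction is partly spatial: which sites carry a signal that goes with analgesia. That is fair, but the signal at those sites is still the one seen under optimised stimulation, a state that does not exist when a lead is being placed.

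Third, the same criticism reaches the remedy. A week-8 recording also comes after lead placement, intraoperative test stimulation of the contact combinations (14.3.4) and general anaesthesia, with possible post-operative pain (14.3.5). Section 8.2 adds that insertion itself may temporarily alter the response. All of this stands. The change improves the timing of the predictor; it does not by itself validate targeting.

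Fourth, Table 2 leaves room for sensing at week 8 and during inactivation. It does, but it requires neither an off-state LFP nor an inactivation. Nor do nine occasions against eight amount to a contradiction.

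A reader might also infer that stimulation pulses contaminate the spectra. The documents give no means of sizing that, and the point does not rest on it.

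**Conclusion.** The concern holds in a limited form. As specified, 0 of 8 recordings precede activation, all are at the pain-optimised setting, and no lag to later pain is stated. The planned analysis can describe correlates under treatment. It could forecast later relief in treated participants if a lagged analysis were added. It cannot test whether a signal present before stimulation predicts efficacy, which is the information most relevant to 11.4 and to the targeting use in 17.2.

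The conclusion assumes that 14.3.4 is the full recording specification; no other section sets a condition. The consequence is confined to one exploratory objective in a PC+S subset of unstated size, at most 12, which 17.2 itself calls preliminary. The change is worth making because it is cheap and the recording cannot be recovered later. Nothing here puts the primary pain or safety conclusions in doubt.

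**What to change.** **Section 14.3.4 and Table 2**
- For PC+S participants, add a one-minute all-contact recording at the existing week-8 programming session, in the off state in which 12.3 already takes the NRS and before the implanted system is activated.
- State in the Table 2 row that week 8 includes sensing.
- Also record whenever an inactivation takes place anyway, without changing when or whether stimulation is stopped.

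**Section 17.2**
- Relate the pre-activation LFP, by contact, to later pain change on the NRS at a week named in advance.
- Describe the on-stimulation recordings as correlates under treatment. If a lagged analysis of them is wanted, write it down and limit its claim to participants already treated.

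**If the recording is declined,** reword the objective in the synopsis and 11.4 from prediction to correlation during treatment, and bring 17.2 into line.

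**Cost.** One extra minute per PC+S participant (8 to 9), or at most 17 minutes in total if inactivations at all eight later visits are used; slight battery use, since 14.4 says sensing affects longevity; and an amendment. No visit is added and stimulation is unchanged. This assumes the device can sense with therapy off, which 9.1 suggests by describing sensing and therapy as separately controlled. Participants already activated when the amendment takes effect cannot supply the recording, and results remain exploratory in a small, single-arm, open-label subset.

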### 12.3 Treatment Groups

One (1) Treatment group. All participants will receive the same treatment (long-term DBS in PAG/PVG) and undergo the same procedural protocol. Ethical considerations forbid a control group that receives implant surgery without stimulation. Hence participants must serve as their own controls.

After internalization of the pulse generator (electronic stimulator) and subcutaneous tunneling of connecting cables to the electrode and 12-48 hours for recovery from this internalization procedure, stimulation will be applied to the patient. The patient will be asked to report their ongoing pain level, on a 0-10 numerical rating scale (NRS) with the stimulation turned off and, for each electrode contact, in small voltage steps up to the threshold for any aversive effects (if not seen in the first step). Floating, dizzy or warm feelings can be expected, based on literature reports. If there is no ongoing pain, cutaneous brushing to cause allodynia below the injury, at sensitive sites determined in the pre-surgical testing sessions, will be used. Blood pressure will also be measured by cuff before and during electrical stimulation. This will be repeated on week 12. The optimal level will be 67% of threshold for aversive or other unwanted effects (e.g. motor) or device maximum (10 V) if such effects are not observed. We expect the optimal voltage to be 4-10V. A frequency range of 10-20 Hz and pulse width range of 250-450  $\mu$ s is anticipated, but these parameters will be set according to the subject's responses. The subject returns home with the optimal stimulation settings after each programming session.

Subjects will receive monthly adjustment of stimulation levels to optimize analgesia on the NRS. They will be given the option of remaining in the study if any level becomes unpleasant in later months.

The subject will be given up to 4 different program groups after study week 16, differing in contacts, voltages, frequencies and pulse widths, all determined to be without adverse effect by the clinician programmer in the in-person office session. The subject is asked to switch program groups using their patient programmer. They switch immediately if relief is unsatisfactory, and stay with the best program for pain relief, or with any adequate program if the best is not determined, keeping a pain diary (score 0-10) at intervals of 24 hours or less to help determine the best program group.

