#### 14.4 Lead and or DBS Removal

These devices have been designed and tested, with FDA approval for certain disorders, to be permanent implants. However, there are occasions in which the device or a portion of the system might need to be removed. If necessary, this requires additional surgery with risk.

The most common reason for removal is infection. At our institution, deep brain stimulation carries a 1.5% risk of infection necessitating removal. The majority of the time, the implantable neurostimulator and extension cables need to be removed with preservation of the intracranial lead. This is a result of the fact that most infections start at the neurostimulator implant site.

Alternative reasons for removal of the system would be patient request in the event that the device does not produce its intended results. However, in this instance, it is rare for patients to request removal as it requires additional surgery and there is no significant risk to keeping the device. Devices may also malfunction or break necessitating removal or revision surgery to fix.

Generators have a lifespan which ends at the time of battery failure. On average generator batteries fail after 3-5 years depending on stimulation parameters. Battery longevity depends also on sensing features. Thus it is expected that the battery of the Activa PC+S 37604 Neurostimulator will last less than that of the Activa PC 37601 (which does not allow for sensing). When considering the stimulation parameters currently being used in the study, the Medtronic reference manual for battery longevity of the Activa PC+S neurostimulation system for DBS estimates the longevity at roughly over 4.5 years. This number only represents an estimate, considering battery longevity depends on several factors: programmed parameters, system impedance, hours per day of stimulation, degree of patient control over programmable stimulation parameters, and the use of sensing features (in the case of the Activa PC+S system). This figure is based on stimulation frequencies >100 Hz as used in movement disorders; it is expected that pain treatment will use lower frequencies (<25 Hz) which will give at least 1-2 years more lifetime according to calculations based on manufacturer's confidential data (M949908A001, System eligibility and battery longevity manual for Activa PC+S). In the event that battery replacement would be needed, routine, same day, surgery is performed to remove and replace the generator.

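### Local field potentials are recorded only with stimulation on, at an anticipated rate inside the analysed bands, so stimulus peaks cannot be told apart from neural ones as the plan is written

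*Combined protocol and SAP*

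**What the plan says.** Section 11.4 makes it a secondary objective to learn whether local field potentials (LFPs) in the target region predict the efficacy of stimulation. Section 12.3 limits this to the participants who receive the PC+S device.

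- **Recording.** Section 14.3.4 schedules LFP recording at weeks 12, 16, 20, 24, 32, 40, 48 and 52: "Recording will be done from all contacts during DBS at optimal setting for pain relief, over a period of one minute". Section 12.6.1 carries the same procedure into the extension.
- **Stimulation.** Section 12.3 anticipates "A frequency range of 10-20 Hz and pulse width range of 250-450" microseconds and adds "We expect the optimal voltage to be 4-10V". It also says that "these parameters will be set according to the subject's responses", and that levels are adjusted monthly to optimise analgesia on the pain scale. Section 14.4 expects rates below 25 Hz.
- **Analysis.** Section 17.2 uses autocorrelation, cross-correlation between leads, and "power in alpha, beta, gamma and delta EEG bands". It continues: "Peaks in spectra or in auto- or cross-correlations will be examined for correlations with pain level", for each contact or pair of contacts. The results are to be assessed for use in placing electrodes in future subjects.
- **Stimulator off.** Table 2 lists a possible five-minute inactivation in the same row as sensing. Section 12.5 uses inactivation to study placebo effects and the safety and stability of the implant. Neither place assigns an LFP recording to it.

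No section states how stimulus artefact is handled, and none gives band limits in Hz. Section 9.1 describes the sensing system without a figure for stimulus rejection.

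**The concern.** A regular pulse train produces spectral lines at its rate and at every multiple of it. It also produces correlation peaks at every multiple of its period. The anticipated rate lies inside the frequency range that Section 17.2 analyses, and the recordings come from the stimulating leads while they stimulate. A peak found there may be neural, may be evoked by stimulation, or may be the pulse train itself. The planned data cannot distinguish these.

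The problem can go beyond added noise. Contacts, voltage and rate are re-tuned to improve pain relief, so any residual artefact depends on settings that were chosen partly on the outcome. An association between LFP peaks and analgesia could then arise without a physiological link and be carried into electrode targeting in later studies.

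**Working it through.** The plan states no figure on this point, so there is none to reproduce. Two checks follow: where the stimulation lines fall, and how large they could be.

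**1. Where the lines fall.** Assumed limits: delta 0.5-4, alpha 8-13, beta 13-30, gamma 30-100 Hz, with 30 and 100 Hz counted in gamma. Lines lie at k × f for k = 1, 2, 3 and so on, and correlation peaks at multiples of 1/f.

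| Rate f (Hz) | Alpha | Beta | Gamma | 1/f (ms) |
|---|---|---|---|---|
| 10 | 10 | 20 | 30 to 100, 8 lines | 100 |
| 12 | 12 | 24 | 36 to 96, 6 lines | 83 |
| 15 | none | 15 | 30 to 90, 5 lines | 67 |
| 20 | none | 20 | 40 to 100, 4 lines | 50 |

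Three bands are touched at about 10-13 Hz. Two are touched from about 13 to 20 Hz, which is 7 of the 10 Hz in the anticipated range. No line falls in delta. At 25 Hz, the upper end of the Section 14.4 expectation, the fundamental is still in beta. Section 9.1 requires programs in one group to share a rate, so two leads driven from one group would also share the period in their cross-correlation.

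**2. How large the lines could be.** For a rectangular pulse train of amplitude A and width w, the line at k × f has amplitude 2·A·w·f·sinc(k·f·w). At these settings the sinc term for the fundamental is about 1.

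- Low end: 2 × 4 V × 0.00025 s × 10 Hz = 0.020 V = 20 mV.
- High end: 2 × 10 V × 0.00045 s × 20 Hz = 0.180 V = 180 mV.

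Assume an LFP of 10 µV rms. The rejection needed to bring the fundamental down to that level is 20·log10[(amplitude/√2)/10 µV]:

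- Low end: 14.14 mV / 10 µV = 1,414, or 63 dB.
- High end: 127.3 mV / 10 µV = 12,730, or 82 dB.

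These figures assume slow charge recovery after each pulse. With symmetric biphasic pulses the need falls to about 27-57 dB. For an LFP between 50 and 1 µV, the slow-recovery range is 49-102 dB.

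The artefact was then added to simulated 60-second backgrounds of 10 µV rms, with power falling with frequency and a bump near 9 Hz. Rates were 10, 13 and 20 Hz. Pulse settings were 4 V with 250 µs and 10 V with 450 µs, with 20 runs per combination and slow recovery.

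| Assumed rejection | Artefact share of 8-30 Hz power |
|---|---|
| 60 dB | 94% to 99.8% |
| 80 dB | 14% to 82% |
| 100 dB | 0.2% to 5% |
| 120 dB | about 0% |

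**3. How settings alone can move the measure.** At 10 Hz and 80 dB, the share was 13.8% at the lower pulse setting and 76.4% at the higher one, with the same background process. Measured power equals background power divided by (1 − share). It therefore rises by (1 − 0.138)/(1 − 0.764) = 0.862/0.236, about 3.7-fold, with no neural change.

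**The case against.** The strongest reply is that overlap does not show dominance. The PC+S is built for sensing, and it may reject the stimulus well enough that little remains. Silence about filtering does not prove that raw artefact would be analysed as brain signal. The LFP work is descriptive, is labelled preliminary, covers a subset, and drives no decision rule. All of this is fair and limits the point.

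Four stronger readings are tempting, and the documents do not support them.

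- **That the peaks will mostly be the stimulus.** This needs the device's rejection, the pulse shape and the LFP amplitude. None is given, and the share spans nearly the whole scale.
- **That three of the four bands are affected in every recording.** Above about 13 Hz no line falls in alpha. The 10-20 Hz range is also anticipated, not fixed.
- **That the LFP objective will get a wrong answer.** Section 12.3 sets the optimal level at 67% of the threshold for unwanted effects, or the device maximum, which is not a pain score. The later adjustments do aim at analgesia, so a link is possible, but its direction and size cannot be derived.
- **That only a peak present with the stimulator off is neural.** This would discard genuine stimulation-evoked activity, which may matter for predicting efficacy.

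What the reply does not answer is that every specified LFP recording is made with stimulation on. If no stimulator-off recording is made, later analysis cannot supply that comparison.

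**Conclusion.** The concern holds in limited form. As written, peaks at the stimulation rate and its harmonics cannot be told apart from neural signal, and residual artefact could create a spurious LFP-pain association. Under the assumed band limits this touches three bands at about 10-13 Hz and two above about 13 Hz. The artefact could make up anything from about 0% to over 99% of 8-30 Hz power, under the assumptions on rejection, pulse shape and LFP size used above. Nothing in the documents narrows that range, which is the reason to fix the handling in advance. The change is worth making because it is cheap and serves a stated objective. The primary pain and safety assessments are unaffected.

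**What to change.** **Section 14.3.4.** Add a one-minute LFP recording from the same contacts with the stimulator off, whenever the inactivation listed with sensing in Table 2 takes place. Stimulation settings do not change.

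**Section 17.2.**

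- Define each band in Hz.
- Exclude the programmed stimulation frequency and its harmonics from band power and peak detection, for example within ±1 Hz.
- Blank the pulses, or subtract a pulse template, before computing auto- and cross-correlations.
- Report LFP-pain associations within participant, with the programmed settings listed for each recording.
- Label a stimulation-rate peak that is absent in the off recording as indeterminate (artefact or stimulation-evoked), and do not count it as a neural predictor.

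**Cost.** One minute of recording in a step that already exists, plus analysis code. The loss of spectrum is not trivial at low rates: ±1 Hz at 10 Hz removes 9-11 Hz, which is 2 of alpha's 5 Hz (40%). At 20 Hz it removes 2 of beta's 17 Hz (about 12%). The lost bins differ with the programmed rate, so band power becomes less comparable between recordings made at different rates. The inactivation is only listed as possible, so some visits may have no off recording; their number should be reported.
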